For very symptomatic V shaped lesions, a resin-modified glass ionomer restoration may be the preferred treatment [9, 10, 12]. This material covers and seals the dentin tubules, providing a protective layer where the cementum has worn away. However, resin-modified glass ionomer restorations do not always reduce or diminish the tooth pain because the chemical makeup of resin-modified glass ionomers themselves may trigger tooth irritation through an inflammatory response in the pulp [13]. Therefore, it is important to evaluate new dental materials that may be more effective in treating the pain associated with tooth sensitivity with fewer negative sequelae. A new biocompatible and bioactive material (Biodentine™) is available. Biodentine™ has a wide range of clinical applications because of its similarity to the dentin and its mechanisms of dentin adherence. Furthermore, Biodentine™ has been successfully used as a safe dentin substitute in clinical studies[14]. However, the effect of Biodentine™ to reduce tooth pain in V shaped lesions is unknown.

We propose to investigate the effect of Biodentine™ as a restorative dental material on V shaped lesions with a randomized single blind controlled study. Specifically, we will investigate how Biodentine™ treatment affects oral health related quality of life. Because Biodentine™ is a biocompatible and a bioactive material, which is considered a dentin substitute material, we hypothesize that Biodentine™ is a more effective way of treating tooth pain associated with V shaped lesions compared to traditional resin-modified glass ionomer restorations. To evaluate the effects of Biodentine™ as a dental restorative material, we will compare the treatment with Biodentine™ to the resin modified glass ionomer, which is a dental material widely used to restore V shaped lesions. In addition, we will evaluate the impact on oral health via patient self-reporting of pain and daily activities with an oral health related quality of life questionnaire before and after treatment at multiple time points.

Specific Aims (SA):

SA1: Investigate whether Biodentine™ is more effective compared to resin-modified glass ionomer in reducing tooth pain in V shaped lesions

SA 2: Investigate whether Biodentine™ is more effective compared to glass resin-modified ionomer in improving general oral health-related quality of life in patients with V shaped lesions.

[figure not shown]

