3 months (+/- three weeks)- Follow-up	OHIP-49 BPI questionnaire PGIC Scale Rationale: We expect an immediate elimination of pain but the impact on OHRQL will be more quantifiable if assessed over time.	OHIP-49 BPI questionnaire PGIC Scale Rationale: We expect an immediate elimination of pain but the impact on OHRQL will be more quantifiable if assessed over time.

Data Collection Procedures

Initially patients will be consented for enrollment and treatment in the study. Data for the clinical study will be collected multiple times during the study including prior to treatment, and 1 week, 2 weeks, and 3 months post treatment. Patients will receive an OHIP-49 questionnaire and a modified BPI and the third survey (PGIC scale) to relate to overall oral health via electronic emails. The surveys will be emailed to the participants via a secure survey source (REDCap) and completed electronically by the participants after their initial visit for the restoration placement. Patients will have 7 days to complete the email surveys and email reminders will be sent daily until the surveys are completed. If patients are unable to complete an emailed survey, they have the opportunity to return to the school to complete the surveys. The UMSoD has a supply of iPads® available for research purposes and will be used to collect data at the initial enrollment and if patients come to the school to fill out follow up surveys. There will be a 3-week window for subjects to return to the school for the 3-month follow-up visit.

Data management

All scanned data that goes to a digital form and acquired digital data will be kept on a secure server at the University of Michigan School of Dentistry that is password protected. A secure patient treatment record will be created with the patients assigned participant number, all paper materials returned from patients and participant consent materials will be kept in a locked cabinet in a locked office at the University of Michigan School of Dentistry..

Statistical Analysis Plan

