Prior to testing primary study aims, we will examine data distribution characteristics to identify outliers and determine suitability of the data for parametric testing. Bivariate correlations will be conducted to identify important covariates for inclusion in main statistical models (e.g. age). Assuming underlying assumptions are met, we will use repeated measures of general linear models (GLM) to test for significant differences between the control and treatment groups in terms of changes in pain (specific aim 1) and oral health related quality of life (specific aim 2) over the course of the study. Significant group versus time effects will be examined graphically to determine the nature of the interaction and to qualify how pain and oral health related quality of life changed over time for each group.

Power Analyses

Currently, we do not have input data available to do an adequate sample size analysis or the study. For this small pilot study, we planned for a sample of 40 participants (20 subjects in control group and 20 in the experimental group) to generate some preliminary data for conducting a rigorous sample size analysis for a larger clinical trial

Potential Problems and Alternatives Strategies

In the event that we do not recruit enough patients to fulfill project timeline, we can recruit patients from the graduate clinic at the University of Michigan School of Dentistry and the emergency clinics.

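### Neither aim has a named visit, contrast or between-arm estimate: a significant group-by-time effect is to be read from a graph, which cannot settle whether Biodentine is better

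*Combined protocol and SAP*

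**What the plan says.** The Specific Aims section poses two superiority questions: whether Biodentine does better than resin-modified glass ionomer on tooth pain (SA1) and on general oral health related quality of life (SA2). The Statistical Analysis Plan section treats both as primary ("Prior to testing primary study aims") and gives one method for both: "we will use repeated measures of general linear models (GLM) to test for significant differences between the control and treatment groups", applied to changes over the study. Its only further step is "Significant group versus time effects will be examined graphically to determine the nature of the interaction", with the graph also used to describe how each group changed.

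Data Collection Procedures and Table 2 give four surveys: baseline, week 1, week 2 and month 3. The month 3 row of Table 2 carries the rationale "We expect an immediate elimination of pain but the impact on OHRQL will be more quantifiable if assessed over time", printed in the columns of both arms.

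On size, the Power Analyses section says "we planned for a sample of 40 participants (20 subjects in control group and 20 in the experimental group"), explains that "we do not have input data available to do an adequate sample size analysis", and gives the purpose as "to generate some preliminary data for conducting a rigorous sample size analysis for a larger clinical trial". No power, significance level, effect size, SD, sidedness or order of aims is stated.

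**The concern.** Each aim asks a question with a direction, but the planned test has none. A group-by-time interaction over four surveys asks whether the two profiles differ in shape in any way. It can be significant when one material is ahead early and behind late, with no net benefit to either. The plan then offers a graph and no rule for turning it into an answer to SA1 or SA2.

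Two things are at stake. First, the reader of the results could pick the visit or feature of the graph that supports a conclusion. Second, the pilot exists to size a later trial, and that needs a named outcome, time point and between-arm difference with its SD. An omnibus F statistic and a plot supply none of these.

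**Working it through.** There is no power figure in the plan to reproduce.

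**Inputs.** From the documents: n = 20 per arm and four surveys. Assumed: two-sided 5% level, outcome SD 1 at every survey, common within-person correlation ρ (compound symmetry), no dropout, no true baseline difference.

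**Formulae.** Let δ_j be the between-arm difference at survey j, with δ = 0 at baseline.
- 3-df interaction: λ = (n/2) × Σ(δ_j − δ̄)² / (1 − ρ), referred to F(3,36) in multivariate form or F(3,114) in univariate form.
- 1-df contrast on mean follow-up change: its variance is 1 + (1 + 2ρ)/3 − 2ρ = (4/3)(1 − ρ), so λ = (n/2) × (mean follow-up δ)² / [(4/3)(1 − ρ)], referred to F(1,38).

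**Step 1: can the interaction be significant with no average benefit?** Take δ = (0, +0.6, 0, −0.6). The mean follow-up difference is 0 and Σ(δ_j − δ̄)² = 0.36 + 0.36 = 0.72.
- ρ = 0.3: λ = 10 × 0.72/0.7 = 10.29, multivariate power 72%.
- ρ = 0.5: λ = 10 × 0.72/0.5 = 14.4, multivariate power 87%.

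So a null answer to the question about average benefit would usually come out as a significant interaction.

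**Step 2: illustration for a constant difference.** Take δ = (0, d, d, d). Then Σ(δ_j − δ̄)² = 0.75d², and the interaction λ is 10 × 0.75d²/(1 − ρ). The 1-df contrast gives the same λ, because 1/(4/3) = 0.75. The 1-df contrast reaches 80% power at λ = 8.27, which is √(8.27/10) = 0.91 SD of the mean change. The same λ gives 62% on F(3,36) and 65% on F(3,114), whatever ρ is.

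**Step 3: effect confined to month 3.** Take δ = (0, 0, 0, 1) and ρ = 0.5. Interaction: Σ(δ_j − δ̄)² = 1 − 1/4 = 0.75, λ = 10 × 0.75/0.5 = 15, power 88%. Mean-change contrast: λ = 10 × (1/3)²/0.667 = 1.67, power 24%. Averaging over visits does not help here; it costs power.

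**Step 4: how far does the illustration travel?** Power of the 3-df test for a constant difference at which the comparator named has 80%, under compound symmetry unless stated:

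| 1-df comparator | Power of 3-df test |
|---|---|
| Mean follow-up change | 62–65% |
| Month 3, baseline-adjusted, ρ 0.3 / 0.5 / 0.7 | 61–64% / 68–72% / 74–77% |
| Follow-up mean, baseline-adjusted, ρ 0.3 / 0.5 / 0.7 | 32–34% / 41–44% / 50–53% |
| Month 3 change score | 81–84% (no loss) |
| Mean follow-up change, correlation decaying with calendar time | 75–90% multivariate, 42–52% univariate uncorrected |

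**Step 5: why the contrast must use baseline.** In the Step 2 scenario, where mean change has 80% power, an unadjusted follow-up mean has variance (1 + 2ρ)/3 and power 96%, 80% and 51% at ρ = 0.3, 0.5 and 0.7. At ρ = 0.7 that is below the 62% of the 3-df test.

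**The case against.** The 3-df reading is an inference. The text speaks of changes. If change scores at the three follow-ups are what is modelled, the group main effect is already the 1-df mean-change contrast and the interaction has 2 df. This stands as an ambiguity, and it is why the point is stated conditionally. It does not rescue the plan: the text does not say that the main effect is the answer to either aim, and the only follow-up step it describes concerns the interaction. Under that reading a constant difference would not appear in the interaction at all.

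A reader might infer that the plan's power falls from 80%. The documents do not support that: they state no power and say none could be computed, so 80% is only a benchmark.

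A reader might also take the Table 2 rationale as predicting a sustained pain advantage for Biodentine. It is printed for both arms and predicts no difference between them. The Innovation section says only that longer-lasting effects are possible. The constant difference is therefore an assumption.

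Nor is it right that the plan has no direction. The aims and hypothesis state one; only the test lacks it.

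Finally, this is a small pilot, so confirmatory machinery is arguably out of place. That is a fair reason not to gate SA2 behind SA1: quality of life is in the trial's title, and the Specific Aims section says "Specifically, we will investigate how Biodentine™ treatment affects oral health related quality of life". It is not a reason to leave the estimate unnamed, because sizing the next trial depends on it.

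**Conclusion.** The point holds in conditional form. What is certain from the text is that no visit, contrast or between-arm estimate is primary for either aim, and that the stated reading of a significant group-by-time effect is graphical. If that effect is the 3-df interaction, it is non-directional and can be significant about 72% to 87% of the time for a crossing pattern with zero average benefit (0.6 SD swings, ρ 0.3 to 0.5).

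The power comparison of 62–65% against 80% is secondary. It rests on a constant difference, compound symmetry, no dropout, and mean change as the comparator. It disappears against a month 3 change score and reverses for an effect confined to month 3. The case for change rests on getting an answer that can be interpreted, not on a power loss in the plan. It should be settled before the outcome data are compared by arm, but it does not invalidate the trial.

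**What to change.** In the Statistical Analysis Plan section, replace the graphical step with one pre-named 1-df contrast per aim from the same repeated-measures model, each reported as an estimate with a 95% confidence interval:
- **SA1:** the between-arm difference in mean change from baseline in pain over week 1, week 2 and month 3 (or the follow-up mean adjusted for baseline).
- **SA2:** the between-arm difference in OHIP-49 at month 3, adjusted for baseline.

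State that the omnibus interaction, the other visits and the graphs are descriptive. No testing order between the aims is needed.

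The change is wording only: no new patients, visits or data. The downside is that a difference confined to one early visit becomes descriptive. A pain difference appearing only at month 3 would also be diluted in the SA1 average (Step 3), so the choice of contrast should be made deliberately and in advance.

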The Role of Biodentine in Class V Dental Lesions on Oral Health Related Quality of Life

NCT03304184

Date last modified: July 13, 2018

SPECIFIC AIMS

More than 45 million adults suffer from overly sensitive teeth in the United States [1] which affects women more than men [2]. Tooth sensitivity leads sufferers to avoid many of their favorite foods because the temperature of the food can lead to a sharp intense pain. Even cold atmospheric air can trigger extreme pain [3]. Tooth sensitivity can be chronic causing a disruption in daily activities of the affected individuals, thereby seriously impacting their oral health related quality of life [4].

Tooth sensitivity occurs when the dentin and dentin tubules that contain fluid along with nerve endings are exposed due to the removal of a protective layer surrounding dentin called cementum. This process of cementum removal is frequently associated with gingival recession caused by aggressive tooth brushing. Improper tooth brushing techniques can cause the toothbrush bristles to act like a saw at the gumline. The saw-like action creates a V shaped lesion thereby exposing dentin [5] (Fig. 1), which is frequently associated with tooth sensitivity [6]. Once the dentin is exposed, the fluid inside the dentin tubules can move by changes in osmotic pressure (Fig. 1C) [7]. This movement leads to perceived pain via activation of nociceptors. For the purposes of this study, we will be referring to tooth sensitivity as tooth pain because of the activation of nociceptors within the pulp [8]. Commonly, patients that suffer from extreme tooth pain associated with V shaped lesions are treated with non-restorative and restorative treatments that include the use of over-the-counter fluoride, prescription fluoride, sensitivity reducing medicaments, toothpastes containing potassium nitrates and restorations with dental materials that cover the affected area [9, 10].

Despite numerous ways to treat tooth pain associated with V shaped lesions, most of them are unsuccessful at reducing the discomfort permanently [11].

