Therefore, this study is innovative because it proposes to evaluate a new bioactive and biocompatible dental material as it relates to diminishing tooth pain. More specifically, our study includes four important innovative aspects: 1) Biodentine™ is biocompatible and bioactive, which may suppress inflammatory pulp responses and promote better marginal seal [25-28]; 2) Biodentine™ relies on the presence of biofluids to form hydroxyapatite crystals [24] [25]; 3) Biodentine™ derived hydroxyapatite crystals (naturally present in the tooth structure) may result in more long-lasting effects on tooth pain [29]. More importantly, 4) we propose to evaluate the impact of V shaped lesions associated tooth pain in our patients' quality of life before and after the proposed alternative treatments.

The lack of guidelines to treat tooth pain associated with V shaped lesions is an important area of study [30, 31]. In addition, despite the many treatments used by clinicians to treat pain in V shaped lesions there is little evidence of their effectiveness [27]. The results of our study will provide evidence to fulfill an enormous lack of

knowledge in the dentistry, which will ultimately help clinicians make appropriate treatment decisions to treat tooth pain associated with V shaped lesions. More importantly our study may contribute to the knowledge of the impact of pain associated with V shaped lesions in the patients' overall quality of life.

Approach

Study Design

The proposed study is a two-year single blind study with blinded assessors to evaluate participant responses about chronic pain from V shaped tooth lesions. The participants will be recruited from the University of Michigan School of Dentistry and will be treated with a traditional dental material and with a new dental material. Participants will fill out screening questions to determine eligibility. Once enrolled they will either receive the traditional treatment for a sensitive V shaped lesion or will be treated with the new material Biodentine™. Participants will be evaluated prior to treatment and post treatment at 1 week, 2 weeks, and 3 months to determine the effects of the two different treatment modalities on OHRQL.

Participants

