Once enrolled, the participants will be randomly assigned to control or treatment group. The control group participants will receive the gold standard treatment for V shaped lesions - a resin modified glass ionomer (Photac-fil®). Treatment group participants will receive their V shaped lesion restoration with Biodentine™. When they receive the restoration, all treatments will follow the standard of care for their placement and polishing at the UMSoD. Participants will be assigned a random number to identify them and will be blinded as to which treatment they will receive. Participants will fill out the same OHIP-49 and BPI questionnaire via a

survey link at 1 week, 2 weeks, and 3 months post treatment. If participants complete the survey, they will receive a monetary compensation of \$10 dollars/group of surveys completed for a potential of \$40 dollars to ensure participant compliance with the survey. Surveys will be completed at recall appointments on a secure survey system maintained by the UM medical school, REDCap and data will be stored on REDCap and backed-up to a secured University of Michigan Server. Expert assessors collecting patient information will be blinded as to the treatment the participant receives. At 3 months, the patients will receive a follow up evaluation of the filling, and an evaluation of the restoration placed at the V shaped lesion. Table 1 gives a visual breakdown of the study design. The restorative materials used in this study will be placed following manufacturer's instructions.

Table 2: Study Design

Timeline	Control Group (group size: 20) Study enrollment assigned random number	Treatment Group (group size: 20) Study enrollment assigned random number
Prescreen	Oral exam, dental prophylaxis, (Part of standard of care at UMSoD) pre-screen questionnaires modified from BPI	Oral exam, dental prophylaxis, (Part of standard of care at UMSoD) pre-screen questionnaire modified from BPI
Day 1 – Baseline	OHIP-49 BPI questionnaire	OHIP-49 BPI questionnaire
Day 1 - Baseline	Treatment: PHOTACFIL®	Treatment: BIODENTINE™
Week 1 - Follow-up (survey will be emailed and should be completed within 7 days)	OHIP-49 BPI questionnaire PGIC Scale	OHIP-49 BPI questionnaire PGIC Scale
Week 2 - Follow-up (survey will be emailed and should be completed within 7 days)	OHIP-49 BPI questionnaire PGIC Scale	OHIP-49 BPI questionnaire PGIC Scale

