In the event that either the control or treatment restoration falls off we will offer to replace the restoration and we will continue the measurement procedures. Due to the locations of the class V lesions, the stresses of the restoration during mastication may promote debonding of the restorations however, Biodentine has an increased risk of debonding. According to the manufacturer, Biodentine bonds well with dentin; however, no studies exist evaluating its bond strength in class V cervical lesions. If the Biodentine debonds, we will place a base layer of Biodentine to cover and seal the dentin and place Photac-fil® over top of that for added retention. This will allow Biodentine to remain in contact with the dentin but be more retentive. If a Biodentine restoration is placed in a shallow lesion that does not have a lot of natural retention, we will automatically place a Biodentine layer that is covered by Photac-fil®. Loss of restorative material will be covered under the grant for up to six months after initial placement of the restoration and will be noted in the patients record. If a participant has a restoration replaced, a new time line will be started for post-treatment evaluations just like a newly placed restoration. Additionally, Biodentine™ is not offered in multiple shades and patients may request that it is covered with a more esthetic restoration after the study is completed at the University of Michigan School of Dentistry (UMSoD).

Project feasibility

The undergraduate clinics have over 5,000 male and female patient visits per month for treatment of patients aged between 18-60. New patients are screened daily at the school and are continuously added to the patient population at the UMSoD. We plan to recruit from the dental undergraduate clinic. While we do not foresee enrollment issues, we can also access over 3,000 more patients in other clinics at the UMSoD by including the graduate clinics and faculty clinic. Given the high numbers of patients seen at the school of dentistry, we do not anticipate any difficulties in recruiting patients to meet enrollment numbers for the study.

Project Management and Project Timeline

The project principal investigator is [name] [name] and co-investigator is [name]. We will train and calibrate dental students to apply the materials as well as collect participant assessments as

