The benefits to the participant are that they will receive at least one free dental restoration, which will potentially reduce or eliminate the tooth sensitivity associated pain. Furthermore, all other patients suffering from tooth pain may also benefit from an alternative, long-lasting and effective solution for tooth pain associated with V shaped lesions. Participants will also be compensated monetarily for the time after completing of each survey time point.

4. Gained Knowledge.

The information gained in this study may improve the treatment and the management of tooth-sensitivity associated dental pain. Additionally, the information gained with this research will specifically enhance the

knowledge of the impact of tooth pain associated with V shaped lesions and patients' oral health related quality of life.

5. Inclusion of Women and Minorities

We anticipate that the participants in this study will come from all counties in Michigan. The participants in this study will be men and women. We expect a very diverse population of Latinos, African-Americans, and Asians in our study as well. The UMSoD receives daily a very diverse population of patients, with different social-economical backgrounds as well. The participants in this study are likely to follow the diverse population of the UMSoD.

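### Restoration loss, expected more often with Biodentine, is noted and then reset by a restarted timeline, but is not analysed, so a good 3-month result could hide failures

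*Combined protocol and SAP*

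**What the plan says.** **Expected loss and its handling.** Potential Problems and Alternatives Strategies states that Biodentine carries a raised risk of debonding and that its bond strength in class V cervical lesions has not been studied. On cover for loss it says "Loss of restorative material will be covered under the grant for up to six months after initial placement of the restoration", and adds that loss is noted in the patient's record. After a replacement, post-treatment evaluation starts again as if the restoration were newly placed. The same section says that measurement continues after a loss. It also describes Biodentine-arm restorations covered with Photac-fil, either from the outset in shallow lesions or after debonding.

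**Outcome schedule.** Under Data Collection Procedures, data are "collected multiple times during the study including prior to treatment, and 1 week, 2 weeks, and 3 months post treatment". The last visit has some latitude: "There will be a 3-week window for subjects to return to the school for the 3-month follow-up visit". The second Study Procedures section adds: "At 3 months, the patients will receive a follow up evaluation of the filling".

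**Analysis.** The Statistical Analysis Plan describes repeated-measures general linear models for change in pain (aim 1) and oral-health quality of life (aim 2). Loss, replacement and the filling evaluation are not mentioned there or in the Specific Aims.

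**Purpose and size.** Power Analyses plans 20 participants per arm as a small pilot, to supply data for sizing a larger trial. Participants allows up to two sites to be filled per person.

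**The concern.** The protocol names a way in which the restoration can fail, expects it more often in one arm and arranges to record it, but does not plan to report it by arm. The restart makes this worse. A participant whose filling is lost and replaced begins a new 1-week, 2-week and 3-month series. If that series supplies the analysed scores, the failure leaves no trace in the comparison. Because more failures are expected with Biodentine, the erasure would favour Biodentine.

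Two things are at stake. A 3-month pain result could look better than the treatment deserves. And the pilot, whose declared purpose is to inform a larger trial, would not report the retention figure that the protocol itself says is unknown for these lesions.

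**Working it through.** **1. The plan's own figure.** 20 + 20 = 40 participants, and Table 3 enrols 10 in each of four quarters, 4 × 10 = 40. These agree. The documents give no alpha, power, effect size, SD or loss rate, so there is no sample-size calculation to reproduce.

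**2. What is recorded against what is analysed.**

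| Item | Recorded? | In aims or SAP? |
|---|---|---|
| Pain (modified BPI) | Baseline, 1 and 2 weeks, 3 months | Yes, aim 1 |
| Quality of life (OHIP-49) | Same times | Yes, aim 2 |
| Filling evaluation | 3 months | No |
| Loss of restoration | Noted in patient record | No |
| Replacement | Triggers a new timeline | No; no rule for which timeline enters the model |

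**3. Effect of the restart on the schedule.** A restoration replaced at the end of the six-month cover would have its last survey at 6 + 3 = 9 months after first placement, but still only 3 months after the replacement. A month-3 score can therefore mean two different things.

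**4. Possible effect on the pain comparison (all inputs assumed).** Take pain of 2/10 with an intact restoration in both arms, 7/10 at loss, and 5% loss in control. If replaced participants are scored only on the new timeline, the arms differ by 0. If each loss is counted at its pain score, the difference against Biodentine is (7 − 2) × (Biodentine loss − control loss):
- 10% v 5%: 5 × 0.05 = 0.25 points
- 20% v 5%: 5 × 0.15 = 0.75 points
- 30% v 5%: 5 × 0.25 = 1.25 points

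This shows the most that could be hidden under these inputs. A score taken at month 3 from first placement, after a successful replacement, would recover only part of it. That is why loss needs its own count.

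**5. Precision of a loss comparison with 20 per arm (counts assumed).** Newcombe interval for d = p1 − p2, with Wilson limits (l, u) for each arm: lower = d − √[(p1 − l1)² + (u2 − p2)²]; upper = d + √[(u1 − p1)² + (p2 − l2)²].
- 6/20 (Wilson 0.145 to 0.519) v 1/20 (0.009 to 0.236): d = 0.25. Lower = 0.25 − √(0.155² + 0.186²) = 0.008; upper = 0.25 + √(0.219² + 0.041²) = 0.473. Fisher's exact p = 0.09.
- 4/20 (0.081 to 0.416) v 1/20: d = 0.15, interval −0.071 to 0.370.
- 0/20 in one arm: exact upper 95% limit = 1 − 0.025^(1/20) = 0.168.

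Exact power of Fisher's test at an assumed two-sided 0.05 is 17% for 5% v 20% and 45% for 5% v 30%. Loss can be estimated with an interval here, but cannot be tested with useful power unless the difference is very large.

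**The case against.** The strongest reply is that this is a 40-person pilot whose hypothesis and aims speak only of being more effective. It tests what it sets out to test, over a period for which Table 2 gives a rationale. Much of that stands.

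A reader might infer that the trial rests on lasting relief and therefore fails its own claim by stopping at 3 months. The documents do not support that. The remark that "most of them are unsuccessful at reducing the discomfort permanently" concerns existing treatments in general. That Biodentine "may result in more long-lasting effects on tooth pain" is one of four innovation points, and the Potential Benefits section says only that other patients "may also benefit from an alternative, long-lasting and effective solution for tooth pain". Both statements about Biodentine are conditional, and neither is an endpoint.

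A reader might also infer that loss is followed to 6 months. It is not: six months is the period of grant cover. No visit or survey is scheduled after month 3 from a given placement, so later losses come to light only if the patient returns. Counting participants who were not seen as intact would understate loss. Nor does Table 3 clearly leave room for six-month data, since it shows intervention continuing in Q7 and places manuscript completion in Q8.

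Finally, loss is not wholly invisible in the planned results, because measurement continues after it and pain from a lost filling may reach the scores. The reply does not answer the missing rule on which timeline is analysed, or the absence of any report of loss by arm.

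**Conclusion.** The concern holds as a gap in reporting and analysis up to 3 months. It rests on the text alone: more debonding is expected in one arm, loss is recorded, the clock restarts after replacement, and the analysis plan is silent on all three. The direction of the possible bias, towards Biodentine, depends on the protocol's own expectation being right and on the restarted series being the one analysed, which the plan leaves open. Its size cannot be derived. The 0.25 to 1.25 pain points and the intervals for 6 v 1 and 4 v 1 rest on assumed loss rates, counts and pain scores.

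The mismatch between a partly durability-based rationale and 3-month follow-up is real but secondary. This is a worthwhile improvement at almost no cost, not a defect that invalidates the pilot.

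**What to change.** Add to the Statistical Analysis Plan:
1. A descriptive outcome: the number and proportion of participants with any loss or replacement, by arm, from first placement to the 3-month visit, with a 95% CI for the difference and no significance test. Sources are the 3-month filling evaluation and the loss notes.
2. The unit of analysis: the participant, with a statement that up to two sites may be filled, so restorations may number up to 2 × 20 = 40 per arm.
3. A separate line for Biodentine-arm restorations covered with Photac-fil, at first placement or after debonding, because one rate for the arm would mix different constructions.
4. A statement that pain and quality of life are also analysed on the timeline from first placement, whatever replacement has occurred, and how restarted series enter the model.
5. Efficacy conclusions limited to 3 months.

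**Cost.** Items 1 to 3 and 5 are wording and tabulation of planned data. Item 4 requires that surveys on the original schedule still be sent after a replacement, at $10 per completed set for the participants affected. The result may look less favourable to Biodentine.

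**Optional.** A 6-month loss figure would need active ascertainment, such as a question on whether the restoration is still present. The existing questionnaires are not described as asking this. Sent to everyone with the same compensation, it would cost at most 40 × $10 = $400, with some late non-response and pressure on the Q8 timetable.
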